4.1 Inclusion Criteria

Subjects must meet all of the following inclusion criteria:

1. Be adult male or nonpregnant female aged ≥ 18 years non-indigenous travelers (e.g., visiting students/faculty or international tourists) affected by naturally acquired acute diarrhea. Diarrhea is defined as the passage of at least 3 episodes of unformed stools in a 24-hour period. Stools are classified as formed (retains shape), soft (assumes shape of container), or watery (can be poured). When using this classification, both soft and watery stools are unformed and abnormal.
2. Have at least 3 episodes of unformed stools recorded within the 24 hours immediately preceding randomization (screening and randomization should occur as closely as possible on the same day, i.e. Day 1).
3. Have at least one of the following signs and symptoms of enteric infection:
 - a. abdominal pain or cramps
 - b. nausea
 - c. vomiting
 - d. fecal urgency
 - e. excessive gas/flatulence
 - f. tenesmus
4. Females of child bearing potential (WOCBP*) must not be pregnant or lactating at baseline visit (as documented by a negative urine pregnancy test with a minimum sensitivity of 25 IU/L or equivalent units of beta-human chorionic gonadotropin (Beta-HCG) at screening and urine pregnancy at baseline. **All female subjects will be considered to be of childbearing potential unless they are postmenopausal. WOCBP are defined as sexually mature women without prior hysterectomy, or who have had any evidence of menses in the past 12 months. However, women who have been amenorrheic for the past 12 or more months are still considered to be of childbearing potential, if the amenorrhea is possibly due to other causes, including prior chemotherapy, antiestrogens, or ovarian suppression. Postmenopausal women (defined as women who have been amenorrheic for at least 12 consecutive months, in the appropriate age group, without other known or suspected primary cause) or women who have been sterilized surgically or who are otherwise proven sterile (i.e., total hysterectomy, or bilateral oophorectomy with surgery at least 4 weeks prior to randomization) are not considered WOCBP. Subjects who have undergone tubal ligation are NOT considered as surgically sterile.*
5. Female subjects of childbearing potential who are sexually active with males, must be willing to use an acceptable form of birth control from the day of the first dose administration to 30 days after the last administration of study drug. For the purpose of this study the following are considered acceptable methods of birth control: oral or injectable contraceptives, contraceptive patches, Depo-Provera®

(Medroxyprogesterone acetate- stabilized for at least 3 months); vaginal contraceptive; contraceptive implant; double barrier methods (e.g. condom and spermicide); Nuvaring vaginal hormonal birth control, intrauterine device (IUD), or abstinence with a second method of birth control should the subject become sexually active. A sterile sexual partner is NOT considered an adequate form of birth control. Otherwise, they are not required to use a birth control method if they are in a same sex relationship.

6. All male subjects who are sexually active with females, must agree to use accepted methods of birth control with their partners, from the day of the first dose administration to 7 days after the last administration of study drug. Please see acceptable forms for "Female" birth control above. Abstinence is an acceptable method of birth control for males. Otherwise, they are not required to use a birth control method if they are in a same sex relationship.
7. Subject must be willing and able to comply with study procedures for the duration of the study.
8. Study subjects must have provided Local Ethics Committee (LEC)/ Institutional Review Board (IRB) approved written informed consent using the latest version of the LEC/IRB informed consent form. In addition, study subjects must sign a Health Insurance Portability and Accountability Act (HIPAA) authorization, if applicable.
9. Subject has to be literate and able to sign the informed consent form (ICF) and complete the Diary

4.2 Exclusion Criteria

Potential study subjects will be excluded if any of the following exclusion criteria are present:

1. Is pregnant, breast feeding, or planning a pregnancy.
2. Immediately prior to randomization has acute diarrhea for > 72 hours.
3. Has :
 - a. fever (≥ 100 °F or ≥ 37.8 °C), or
 - b. hematochezia (blood in stool), or
 - c. clinical findings suggesting moderate or severe dehydration.
4. Has active, uncontrolled, or clinically significant diseases or disorders of the heart, lung, kidney, gastrointestinal (GI) tract (other than infectious diarrhea in travelers), or central nervous system.
5. Administration of any of the following:
 - a. any antimicrobial agents with an expected activity against enteric bacterial pathogens within 7 days preceding randomization.

- b. more than two doses of a symptomatic antidiarrheal compound such as antimotility agents, absorbent agents, and antisecretory agents preceding randomization.
 - c. any nonsteroidal anti-inflammatory drug or fever-reducing agent, such as aspirin or ibuprofen, which can cause GI bleeding within 8 hours preceding randomization. Acetaminophen or paracetamol is acceptable.
 - d. Use of opioids (in any form) within 48 hours preceding randomization.
6. Has a history or presence of allergic response to rifaximin or related drugs.
 7. People who have lived in or stayed in the country where they acquired travelers' diarrhea for more than 6 months.
 8. Has a history of lactose or gluten intolerance.
 9. Consumed more than 2 alcoholic drinks within 12 hours before screening. Alcohol consumption is not allowed during the study.
 10. Has a current or recent history (within 12 months of screening) of drug or alcohol abuse.
 11. A positive urine drug screen test in the absence of therapeutic use will exclude the subject from participating in the study at the investigator's discretion.
 12. Family members of the investigator and the independent dispenser/unblinded staff member, nor site staff of this study.
 13. Subject currently enrolled in any other clinical investigation or who has participated in any clinical investigation within 30 days prior to starting this study.

4.3 Restrictions

The following are not allowed in this study:

- Any antimicrobial agents with an expected activity against enteric bacterial pathogens within 7 days preceding randomization and during the study.
- More than two doses of a symptomatic antidiarrheal compound such as antimotility agents, absorbent agents, and antisecretory agents preceding randomization and during the study.
- Use of any drug such as aspirin or ibuprofen (Advil), which can cause GI bleeding within 8 hours preceding randomization and during the study. Note: Acetaminophen (Tylenol) or paracetamol is acceptable for use during the study.
- Opioids (in any form) within 48 hours preceding randomization and during the study.
- Alcohol or probiotics consumption

4.4 Withdrawals and Replacement of Subjects

Subjects may be discontinued from study treatment and assessments at any time. Subjects are also free to discontinue their participation in the study at any time, without prejudice to further treatment.

Study completion or discontinuation and the reason for discontinuation will be documented. Possible reasons for a subject discontinuing participation in the study are:

- AE(s) that endanger the health of subjects, making it ethically unacceptable to continue
- Deterioration of the subject's clinical condition(s) that requires appropriate therapy/treatment during the study period
- Lack of efficacy
- Withdrawal of consent
- Lost to follow up
- Death.

In case of an AE, the subject is to be followed up until resolution of the AE. Subjects who discontinue prematurely from the study will not be replaced. Investigational products and study materials should be returned by the subject.

5. Treatments

5.1 Description of Treatment(s)

The treatments used in this study are the following:

- Rifaximin 200-mg tablets (test product) manufactured by Actavis Laboratories FL, Inc.
- Xifaxan[®] 200-mg tablets (reference product) of Salix Pharmaceuticals, Inc. (Valeant Pharmaceuticals group of company)
- Placebo tablets manufactured by Actavis Laboratories FL, Inc.

Rifaximin is marketed under the tradename Xifaxan[®] (Salix Pharmaceuticals, Inc, recently acquired by Valeant Pharmaceuticals). The investigational drug evaluated in this study is generic rifaximin.

5.2 Selection and Timing of Dose for Each Subject

Each subject will receive the same dosing regimen of 1 tablet TID (morning, noon and evening) for 3 days, which is the recommended dosing regimen for Xifaxan[®].

Subjects who take 3 doses of study drug on Day 1 (i.e., those randomized early in the day on Day 1) will complete study drug on Day 3; other subjects will receive the last dose of study drug on Day 4.

5.3 Method of Assigning Subjects to Treatment Groups

Subjects will be randomly allocated [REDACTED] to treatment groups to receive the Test product or the Reference Product or the Placebo control, respectively. The randomization schedule for this study will be generated by a third party vendor of the CRO such that a non-study-assigned independent expert will allocate the subjects to one of the three treatment arms using a computer generated automated process i.e. Interactive Web Response System (IWRS).

[REDACTED]

Study sites should have an unblinded dispenser/unblinded study staff member assigned to maintain blinding throughout the study. Subject must return the study treatment bottle with original carton to the unblinded study staff member.

5.4 Unblinding

In case of emergency, if the detail of study drug is required for management of emergency as per the opinion of investigator, investigator can unblind the product that is received by the patient during the study. In case of non- emergency condition that requires study drug information for management of condition as per investigator's opinion, investigator should obtain sponsor or medical monitor approval in writing prior to breaking of the blind. [REDACTED]

[REDACTED] It is recommended that all attempts should be made to maintain the blind of the study. However, in case the unblinding is performed, the reason for breaking the blind must be clearly documented in the source documentation and electronic case report form (eCRF) and the patient must be discontinued from the study.

5.5 Packaging and Labeling

Packaging and labeling will be carried out in accordance with the requirements of the Good Manufacturing Practice (GMP) guidelines, International Conference on Harmonisation (ICH) Good Clinical Practice (GCP) requirements, sponsor approved standard operating procedures (SOPs) and all applicable country specific laws. A detailed packaging and labelling plan will be put in place with country specific requirements.

Final labeling and packaging of the products will be performed by

[REDACTED]
Actavis Laboratories UT, Inc.
[REDACTED]

in accordance with their SOPs and international requirements. Product labels comply with United States (US) regulatory requirements and languages, and in the case of other participant countries will comply with applicable local regulatory requirements.

5.6 Retention Sample Selection, Storage and Accountability

Retention of Reserve Samples

For every study product shipment received at the Investigator site, the Investigator (or designee) will randomly select at least one block of study product for retention, unless otherwise instructed by the Sponsor and/or CRO. The selection process will ensure a sufficient amount of retention samples are retained as per Sponsor requirement, and the same will be documented. [REDACTED]

The number of each block kept for retention will be noted on the drug accountability form as

a retention sample, in addition to the retention sample log. These retention samples should be stored under the appropriate storage conditions for a minimum of 5 years following the application approval or, if not approved, at least 5 years after the completion of the study. Retention samples should not be returned to the sponsor at any time. The retention samples can be shipped to a third party storage facility. A detailed investigational product plan will be provided to the study site.

Product storage and dispensation

All study material, together with necessary documentation, will be supplied to the study site before starting the trial. The study site will acknowledge receipt of all study material in IWRS.

All supplies will be maintained under adequate security by the clinical investigator or unblinded study staff member/independent dispenser, who will be responsible for all supplies.

The study drugs are to be stored at 20° to 25°C (68° to 77°F) with excursions permitted from 15° to 30°C (59° to 86°F).

The study drugs are to be dispensed only under the restricted conditions defined in the present protocol.

Any test materials remaining at the end of the study will be returned to the designated drug depots or destroyed in accordance with the guidelines provided by Sponsor. Before destruction, detailed product accountability has to be performed. An official document on what has been destroyed has to be issued and sent to the Sponsor/CRO.

Product accountability

Each center will be responsible for maintaining an accurate log and inventory of study material received and returned to the designated drug depot.

At the end of the study, it must be possible to reconcile delivery records with records of used and returned study treatments. An account of any discrepancies has to be provided.

The designated CRO will provide the framework for documenting study treatment accountability, without breaking the blind, throughout the study. CROs will assign unblinded CRAs to perform the drug accountability.

The investigator has to maintain an accurate written record of the shipment, retention, dispensing, and return of study treatments using a drug accountability form. An accurate record of the date and amount of study drug dispensed to each subject has to be available for inspection at any time. The designated CRO representatives will verify drug accountability during routine site monitoring visits without breaking the blind. The total drug accountability will also be performed at the completion of the trial.

At the conclusion of the study and as appropriate during the course of the study, the investigator will return all used and unused drug containers, drug labels, and a copy of the completed drug accountability form to the Sponsor/designee. Some sites may destroy medications locally at an appropriate time point, if previously agreed with the sponsor.

5.7 Treatment Compliance

Subject compliance will be primarily monitored by counting the study tablets dispensed (Visit 1) and returned (Visit 3) compared to diary entries. The medication dispensed and/or returned will be recorded by the independent dispenser/unblinded study staff member in the subject drug accountability log and eCRF. Subjects will be asked to return all original packaging and unused study drug at Visit 3. Compliance calculation will be based on number of tablets taken (as recorded in the study diary) vs number of tablets subjects are expected to take.

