6.3 Treatment

Days 2 to 4

Subjects are to take 1 study drug tablet TID (morning, noon and evening) for 3 consecutive days for a total of 9 doses. Subjects who take 3 doses of study drug on Day 1 (i.e., those randomized early in the day on Day 1) will complete study drug on Day 3; other subjects will receive the last dose of study drug on Day 4. Subject will complete study diary until last study visit day, beginning on Day 1. Subjects will record the following in the study diary:

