10.9 Protocol Violations/Deviations

When a variation from the protocol is deemed necessary for an individual subject, the Investigator or other physician in attendance must contact the Sponsor's Medical Monitor or sponsor representative through the CRO representatives.

Such contact must be made as soon as possible to permit a decision as to whether or not the subject is to continue in the study. The deviation from the protocol will be authorized only for that subject.

All deviations related to study inclusion and exclusion criteria and significant deviations to subject management and protocol procedures must be documented on the appropriate eCRF.

Major protocol deviations/violations will include, but are not limited to, the following:

- Did not meet any critical inclusion/exclusion criteria which may impact the assessment of treatment efficacy.
- Did not receive randomized treatment (i.e., the actual treatment is not randomized treatment).
- Use of prohibited concomitant medications (e.g., prescription or OTC anti-diarrheal drug product, NSAIDs [with the exception of acetaminophen and paracetamol] or opioid analgesics).
- Did not meet the drug compliance of taking ≥ 7 to ≤ 11 doses.
- Did not come for Visit 3 within the visit window period of 24 to 72 hours of last dose.

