### 7.3 Exposure and Treatment Compliance

Subject compliance will be primarily monitored by counting the study tablets dispensed (Visit 1) and returned (Visit 3) compared to diary entries. Compliance calculation will be based on number of tablets taken (as recorded in the study diary) vs number of tablets subjects are expected to take.

Total extent of exposure to study drug will be measured by total number of tablets taken and duration of exposure calculated as date of last dose minus date of first dose plus 1. Study drug compliance (%) will be calculated as number of tablets taken divided by number of tablets expected to take multiplied by 100. Subjects are considered to have good compliance if the compliance (%) is within the range of ~75% to ~125%, corresponding to 7 to 11 doses.

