#### **8.6 Protocol deviations**

The following describes the protocol deviations that relate to statistical analyses or Per-protocol population.

All deviations related to study inclusion and exclusion criteria and significant deviations to subject management and protocol procedures must be documented on the appropriate eCRF. Major protocol deviations/violations will include, but are not limited to, the following:

- Did not meet any critical inclusion/exclusion criteria which may impact the assessment of treatment efficacy.
- Did not receive randomized treatment (i.e., the actual treatment is not randomized treatment).
- Use of prohibited concomitant medications (e.g., prescription or OTC anti-diarrheal drug product, NSAIDs [with the exception of acetaminophen and paracetamol] or opioid analgesics).
- Did not meet the drug compliance of taking  $\geq 7$  to  $\leq 11$  doses.
- Did not come for Visit 3 or did not provide efficacy data for 24 hour to 48 hour period after the last dose.

A list of protocol deviations will be compiled prior to database closure for the primary analysis

and be updated prior to the analysis. The deviations will be listed on randomized population and also will be summarized on randomized population by treatment group.

[figure not shown]
Further, all the protocol deviations will be manually reviewed by the medical monitor of the study to determine whether any deviation is significant with respect to per-protocol population. Such deviations which may affect the treatment evaluation would be declared as “significant” protocol deviation by the medical monitor, and consequently these subjects will also be excluded from the per-protocol population for the primary efficacy analysis, in addition to above mentioned protocol deviations.

The medical monitor will send the significant protocol deviations to Biostatistics team in an excel sheet through email before DB lock. All these significant protocol deviations will also be submitted to regulatory in the form of XPT file along with the protocol deviations captured in the eCRF. The additional list of these protocol deviations will be prepared with respect to per-protocol population criteria and will be listed on randomized population by treatment group.

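### Compliance, on which the 7 to 11 dose criterion for the PP set appears to rest, is calculated from the diary alone, so a subject whose returned tablets rule out 7 doses can still meet it

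*Protocol*

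**What the plan says.** Two sources of dose information are collected. On monitoring, Protocol 5.7 says: "Subject compliance will be primarily monitored by counting the study tablets dispensed (Visit 1) and returned (Visit 3) compared to diary entries". The unblinded dispenser records both tablet counts "in the subject drug accountability log and eCRF", so they are available as data.

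The calculation uses only the other source. Protocol 5.7 says: "Compliance calculation will be based on number of tablets taken (as recorded in the study diary", set against the number expected. SAP 7.3 repeats the protocol rule: "Compliance calculation will be based on number of tablets taken (as recorded in the study diary) vs number of tablets subjects are expected to take". Nine doses are expected (Protocol 6.3: "for 3 consecutive days for a total of 9 doses"), and compliance is good when it lies "within the range of ~75% to ~125%, corresponding to 7 to 11 doses" (SAP 7.3; the same range is in Protocol 9.5).

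The same 7 to 11 range is then a major-deviation criterion in Protocol 10.9: "Did not meet the drug compliance of taking ≥ 7 to ≤ 11 doses". SAP 8.6 lists it under the introduction "The following describes the protocol deviations that relate to statistical analyses or Per-protocol population" and treats the listed deviations as grounds for leaving the PP set. Neither list names the data source for the dose count. The PP set is the primary set for bioequivalence (Protocol 9.2 and the PP section of the SAP).

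**The concern.** The two sources can disagree, and they are not equally informative. If the counts are right, a subject cannot have swallowed more than dispensed minus returned. Lost or discarded tablets only make that figure too large. A high return count is therefore firm evidence of low intake, and no diary entry can outweigh it. A low return count proves nothing. The stated rule ignores the source in the one situation where it is decisive.

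The dose criterion exists to keep under-dosed subjects out of the PP comparison. If such subjects remain in both active arms, each arm's cure rate moves towards the untreated rate and the arms look more alike. In an equivalence test that error favours the sponsor's claim.

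**Working it through.** **1. The plan's own range.** Compliance % = 100 × tablets taken / 9. The limits are 0.75 × 9 = 6.75 and 1.25 × 9 = 11.25, so whole doses run from 7 (7/9 = 77.8%) to 11 (11/9 = 122.2%). Six doses (66.7%) and twelve (133.3%) fail. The stated 7 to 11 range reproduces.

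**2. Where the two sources conflict.** Upper limit on doses taken = dispensed − returned. The number dispensed is visible only in the protocol's summary of changes (12, entry for Section 6.2); the matching current text is redacted. I therefore treat 12 as an assumption and show 9 as an alternative.

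| Dispensed | Returned | Most that could be taken | Compliance at most | Compliance if diary shows 9 |
|---|---|---|---|---|
| 12 | 5 | 7 | 77.8% | 100% |
| 12 | 6 | 6 | 66.7% (fails) | 100% (passes) |
| 9 | 2 | 7 | 77.8% | 100% |
| 9 | 3 | 6 | 66.7% (fails) | 100% (passes) |

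The conflict does not depend on which number was dispensed.

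**3. Direction of the bias.** Let a fraction f of each active arm's PP set be hidden non-takers with untreated cure rate p0. Each arm's rate becomes (1 − f)p + f·p0, and the difference becomes (1 − f)(pT − pR). This assumes the same f in both arms.

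**4. Size on assumed rates.** The planning cure rates are redacted, so these inputs are assumptions: pT = 0.55 and pR = 0.75 among takers, which puts the truth on the margin, and 175 per arm. The 175 is 618 × 0.85 / 3, which is the mITT size under equal allocation; the PP set may be smaller.

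The interval is that of SAP 7.5.1: (PT − PR) ± [1.645 se + (1/NT + 1/NR)/2].

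- At f = 0: se = √[(0.55 × 0.45 + 0.75 × 0.25)/175] = 0.0499.
- The half-width is 1.645 × 0.0499 + 1/175 = 0.0820 + 0.0057 = 0.0877.
- The lower limit clears −0.20 when the observed difference exceeds its expectation by 0.0877/0.0499 = 1.76 standard errors, a probability of about 3.9%.

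Exact enumeration of the two binomials gives, for p0 = 0.55:

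| Hidden non-takers | True difference | Equivalence passed, 175 per arm | Equivalence passed, 140 per arm |
|---|---|---|---|
| 0% | 0.200 | 3.9% | 3.8% |
| 2% | 0.196 | 4.6% | 4.4% |
| 5% | 0.190 | 5.9% | 5.4% |
| 10% | 0.180 | 8.7% | 7.6% |

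At 175 per arm the figure reaches 5.0% at 3% contamination, about 5 subjects per arm (0.03 × 175 = 5.25).

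**5. Adding the placebo requirement.** Both products must also beat placebo at two-sided 0.05. The chance of passing all three tests was enumerated at 175 per arm, using the same active-arm subjects in both analyses as a simplification:

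- Untreated rate 0.55: about 0.5%, 0.7% and 0.9% at 0%, 5% and 10% hidden non-takers.
- Untreated rate 0.35: 3.9%, 5.9% and 8.6%.

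In the first case the test product is no better than placebo, so the superiority test nearly always stops it. In the second it gives almost no protection.

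**The case against.** The strongest reply is that the controls already exist. The count is to be compared with the diary (Protocol 5.7). Source verification covers the diary and drug accountability (Protocol 8), discrepancies in supplies must be explained (5.6), and monitors query doubtful data (10.6). Under SAP 8.6 the medical monitor reviews all deviations before lock and can remove more subjects from the PP set. The PP definition is redacted and the content of SAP Appendix II, which holds the PP logic, is not reproduced.

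Much of this stands. A reader might infer that such a subject is bound to enter the bioequivalence set; the documents do not show that. They show only that the subject meets the criterion as calculated. Nor do the controls close the gap. No visible text makes a mismatch between diary and count a deviation, although the deviation lists are open-ended, and a nine-dose diary does not trigger the dose deviation. If Appendix II does use the count, it departs from SAP 7.3 and the two need reconciling.

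It is also fair that contamination of several percent is speculative. It requires people to over-record doses and then hand back the tablets that contradict them. The documents give no rate. Giving every such subject zero drug effect also overstates the dilution, since some will have taken several doses.

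One objection to the remedy fails: that taking the smaller figure could hide excess intake, as with 12 diary doses and 3 tablets returned. If 12 were dispensed, at most 9 can have been taken, so the diary is the figure that is wrong.

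**Conclusion.** The concern holds as a gap in the calculation rule. Both documents base compliance on the diary although a firm upper limit on intake is recorded, and no visible rule says which source governs when they disagree. Affected subjects can enter the PP set; that they do is not established.

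With equal contamination in the two active arms the bias is towards equivalence. It is small when such subjects are rare: about 4.6% at 2% contamination, against 3.9% with none. The equivalence-only error passes the nominal 5% once contamination exceeds about 3%. A reader might take 5.9% or 8.7% as the trial's overall risk of a false claim. That does not follow, because the placebo requirement can cut the risk below 1%, depending on an untreated rate that the visible text does not give. All these figures rest on the assumed cure rates, arm sizes and zero drug effect in hidden non-takers. The point merits a change because the remedy is cheap and the present rule gives a figure that the trial's own data can disprove.

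**What to change.** In SAP 7.3 and the PP derivation logic (Appendix II), with Protocol 5.7 aligned, and before unblinding:

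- When the bottle is returned, set doses taken to the smaller of the diary count and (tablets dispensed − tablets returned). When it is not returned, use the diary count.
- Apply the existing 7 to 11 criterion and the compliance percentage to that figure. The criterion itself does not change.
- Tabulate by arm the subjects in whom the two sources disagree, and how many change PP status as a result.

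The cost is one derivation line and one table, since both inputs are already in the eCRF. A few subjects may leave the PP set, with a slight loss of precision. Discarded tablets remain undetected, because the count only limits intake from above.
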